6. HUMAN SUBJECT CONSIDERATIONS

6.1 Anticipated Benefits

This study does not offer direct benefit to participants but is likely to yield important information about the optimal approach to diagnose and manage low-intermediate risk patients presenting with possible coronary artery disease.

6.2 Risks and Discomforts

The risks are expected to be the same as if patients underwent the procedure while not a part of a research study. The only investigational component of this trial involves the performance of a modified pre-CCTA non-contrast calcium scan in lieu of a standard coronary calcium study. The performance of the modified calcium scan may lead to diminished accuracy of CCTA and this possibility is being investigated by this study. If the quality of the study is to the degree that the clinic question cannot be answered this study can be associated with additional tests which could include: a myocardial perfusion scan, a stress echocardiogram or a repeat CCTA. An additional CCTA or a myocardial perfusion scan could increase a patient's radiation exposure but overall radiation exposure is expected to be lower. The possibility of additional studies are also possible in the standard CCTA protocol. Otherwise the risk and discomforts are those intrinsic to the clinically indicated CCTA.

The possible risks and discomforts in patients undergoing a clinically indicated CCTA include:

Radiation

During this research protocol patients will be exposed to radiation from a scheduled calcium and coronary CT scan. The total exposure resulting from these imaging studies is calculated to be approximately 2-8 mSv. This is more than they would receive from one year of natural exposure in the Washington D.C, Maryland, Virginia area which is approximately 1.6mSv. Cumulative

exposure from radiation may increase their risk for developing certain types of cancer in the future.

The primary investigator for the research protocol has determined and verified that all of the imaging prescribed for this study would typically be performed as part of the standard medical care required to adequately monitor your current illness in accordance with the ACCF/SCCT/ACR/AHA/ASE/ASNC/NASCI/SCAI/SCMR Appropriate Use Criteria for Cardiac Computed Tomography and is considered standard of care. Non-radiation producing risk stratification alternatives include: exercise stress testing and echo dobutamine and exercise stress testing but these tests were not deemed appropriate by the prescribing physician based off of their clinical assessment.

Pregnant women will not undergo this study due to the risk of harm to the unborn child from the radiation used during this study. A urine or serum pregnancy test will be obtained within a week of the study for child-bearing women. Patients will also be encouraged to inform the physician, nurse or CT technician if there is any possibility of pregnancy.

Intravenous Contrast

Patients will receive intravenous iodine-based contrast for the coronary CT angiography. Most patients tolerate intravenous contrast well but may experience nausea, vomiting, headache, pruritis, flushing, urticaria, wheezing, changes in blood pressure, dyspnea, contrast induced nephropathy, angioedema and anaphylaxis. Patients with a history of severe reaction to contrast (anaphylaxis) have been excluded from this study. Patients with pruritis and urticaria in the past will be treated with prednisone and benadryl (prednisone 50mg given thirteen hours, seven hours and one hour prior to the CT with a concomitant 25-50mg dose of Benadryl given one hour prior to the CT) to prevent a reaction. These patients will be monitored in the CVIR prep and recovery and will have an escort provided by the patient to take them home. Moreover, all patients will have a serum evaluation of their urea nitrogen and creatinine within thirty (30) days of the cardiac CT to decrease their likelihood of contrast induced nephropathy.

IVs are routinely placed by the nurses and technician and are usually well tolerated by the patient but risks include: induration, thrombophlebitis, pain, discomfort, bruising and infiltration of saline or contrast.

Medications

Patients will be given an AV nodal blocking agent to achieve their target heart rate. Typically these medications are well tolerated but are not without risk. These risks include: hypotension, bradycardia, dyspnea, wheezing, fatigue, diarrhea, GI disturbances and worsening of certain neurologic conditions. Patients will be evaluated by a board certified physician prior to

prescribing these medications and they will be monitored prior to and after the procedure by nursing staff in the CVIR prep and recovery location with vital signs.

Patient will also receive Nitrolingual PumpSpray (nitroglycerin lingual spray) to cause vasodilatation to increase blood flow through the arteries to allow for better imaging of the coronary vessels. This medication is typically well tolerated but is not without risk to include: hypotension, headache, dizziness, parasthesia, dyspnea, pharyngitis, rhinitis, peripheral edema, asthenia and abdominal pain. Patients will be evaluated by the cardiologist with vital signs prior to administration of this medication by the nurse and will be monitored after the procedure by nursing staff in the CVIR prep and recovery location with vital signs.

Diagnosis of Disease

Although the calcium scoring and coronary CT angiography will focus on the heart other structure in the chest will be visualized and evaluated with this study. These findings include: pulmonary nodules, hepatic cysts, lung cancer, pneumonia, atelectasis, bony structure abnormalities. Diagnosis of these findings may incur more imaging, follow-up, and invasive testing for the patient. Furthermore, they may also bring emotional and psychological distress to the patient. All non-cardiac findings will be evaluated by a credential radiologist and clinical information will be provided to the patients' primary care manager to ensure appropriate clinical disposition of this findings.

During this study patient's will also receive a diagnosis of their degree of coronary artery disease which may incur more imaging, follow-up and invasive testing for the patient. These finding may also bring emotional and psychological distress to the patient. All cardiac findings will be evaluated by a cardiologist and will be disposition appropriately based off of the clinical information available. There is also an extremely low risk of false diagnosis as with all studies and test but is unlikely due to the high sensitivity and specificity of coronary CT angiography (sensitivity of 96%, specificity of 86%, positive likelihood ratio of 6.38 and negative likelihood ratio of 0.06).

Phlebotomy

Having blood drawn may cause some pain. A bruise may form where the needle enters the vein. Drawing blood may cause some people to faint.

There may also be side effects, other than listed above that we cannot predict, some of which may be life-threatening. Other drugs will be given to make side effects that occur less serious and less uncomfortable. In some cases side effects can be serious, long lasting or permanent.

Should an adverse reaction requiring further treatment or an unforeseen complication arise, appropriate medical care and/or consultation will be provided.

6.3 Actions to Minimize Risks

a. Safety Monitoring Plan

Safety of participants is of primary concern to study investigators, and every effort to avoid adverse events (AE) will be made. An AE will be defined as any unfavorable and unintended sign, symptom, or disease temporally associated with the study procedures, whether or not considered related to the procedure. Only symptoms/signs that begin, increase in frequency or worsen in severity after the procedure start will be considered as AEs. Any asymptomatic change from baseline such as results from diagnostic procedures (renal function or vital signs that is clinically significant (e.g., requires diagnostic or therapeutic intervention beyond confirmation alone) will be considered an adverse event.

CCTAs performed for this study are clinically indicated as designated by their primary cardiologist, and while risk is minimal for CCTA performance, all potential safety efforts will be employed. CCTA examination will be prescribed, performed and under the direct supervision of a study physician. Adverse effects of any CCTA exam (not specific to the choice of tube voltage) may include contrast reaction, impairment of renal function (by contrast dye) and exposure to small amounts of ionizing radiation. Patients will be screened for a history of contrast reaction. If a patient develops a contrast reaction, a fully equipped crash cart and ACLS-trained nurses will be present to administer appropriate care. Impairment of renal function will be avoided by the use of an iso-osmolar contrast agent as well as preferred selection for performance of CCTA. CCTAs will be performed by prospective ECG triggering as a first-line mode, given its merits for lowering radiation dose. Estimated radiation dose for prospectively ECG triggered scans is between 2-8 mSV.

Study personnel will remain vigilant for the occurrence of AEs, particularly those that may be life threatening. Personnel who are trained in the acute management of contrast anaphylaxis and other emergencies and who have access to appropriate clinical supplies will be immediately available while the subject is confined to the CT suite. All study individuals will be closely observed and questioned for any kind of AE at the start and throughout the performance of any CCTA study procedure with non-leading questioning (e.g., “How do you feel?”). The subjects will be instructed to immediately report any symptoms and signs to the study staff (i.e., between formal observations).

All AEs will be evaluated using acceptable diagnoses, if possible. The intensity of all AEs will be graded as mild, moderate, or severe using the following definitions:

- Mild: Tolerable.
- Moderate: Interferes with normal activity.

- Severe: Incapacitating (causes inability to perform usual activity/work).

Study investigators will be instructed to closely monitor each subject who experiences an AE (whether directly ascribed to the cardiac CT procedure or not). Further, study investigators will be vigilant for unexpected AEs, which will be defined as:

- An AE that has not been previously reported for the investigational product (VCT scanner), any procedure medications, or any concurrent medications.
- An AE that is documented in the device or product labeling but is occurring with unexpected severity or frequency.

If an AE has already been reported it will not be necessary to report each individual sign and symptom of that AE as a separate AE. For example, if myocardial infarction is reported as an AE, there will be no need to report elevated creatinine phosphokinase and abnormal ECG, or other related signs, symptoms, or laboratory values as separate AEs. However, if both occur in isolation and myocardial infarction was not diagnosed, then each event would be reported as an AE.

Serious adverse events will also be described, and will be defined as any AE that:

- Result in death.
- Is immediately life threatening.
- Requires inpatient hospitalization or prolongation of existing hospitalization.
- Results in persistent or significant disability or incapacity.
- Is another important medical event.*

** Other important medical events are those that may not have resulted in death, been life threatening, or required hospitalization, but may be considered an SAE when, based upon appropriate medical judgment, they may jeopardize the subject and may require medical intervention to prevent one of the outcomes listed above.*

Unexpected AEs and SAEs will be recorded if they occurred as follows: After a subject starts his/her cardiac CT procedure and throughout the subject's post administration period, whether or not considered related to the procedure; and after the subject's post-administration, and for which a causal relationship to the procedure cannot be ruled out. The research monitor will also look for any difference in AE rates between the two arms to ensure no undue harm has occurred in the research or control arm. A summary of AEs and SAEs will be immediately forwarded the

Independent Ethics Committee/Institutional Review Board (IEC/IRB) and local health authorities, according to local regulations.

b. Safety Analysis Plan

The medical monitor will be responsible for approving the protocol prior to study initiation and for reviewing any adverse events during the study period. Should any adverse events occur, the medical monitor will provide a summary of contributing circumstances to the investigators and the IRB, with recommendations for continuing enrollment (with or without protocol modifications), or for the termination of the study, if needed.

c. Confidentiality Protection

Case report forms and study documents will be stored in a locked cabinet in a secure, locked room (Cardiology Service). When a patient enters the study, they will be assigned a unique patient identification number that is not any part of their social security number. The study identification number will be assigned consecutively as the patient is enrolled into the study. This study identification number will be attached to the patient's data file. The link between the subject number and subject identifying information (master code) will be kept in a locked file in the principal investigator's office in the Walter Reed Cardiology Clinic. The research team in the Cardiology Service will keep the research data for three years from the date the study is closed, and consent form and HIPAA authorizations will be retained for 6 years after the end of the study. At that time all the information will be destroyed. The master code will be destroyed as soon as all data collection is completed.

d. Certificate of Confidentiality

N/A

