5.5 Study Methodology/Procedures

5.5 Methods:

The FOCUS-CCTA study will be a prospective, randomized single center single cohort study to evaluate the diagnostic and clinical implications of modified scan length calcium scoring versus the standard scan length calcium scoring in CCTAs using a MDCT scanner. Significant diagnostic and clinical implications include the quality of the study in the modified versus standard scan length; changes in the cardiac CT after evaluation of the modified or standard calcium scoring (These changes include: a change in mA by 50, any change in kV, any changes

in padding and changing to high definition.); cancellation of the study and a comparison of the radiation received by each patient.

CCTA Study Design:

Patients who are scheduled for CT coronary angiography for evaluation of clinically suspected coronary artery disease who are fifty years old or older without known coronary artery disease and without a previous calcium score will be prospectively included in this study. The indications for CT coronary angiography will be used in accordance with the ACCF/SCCT/ACR/AHA/ASE/ASNC/NASCI/SCAI/SCMR Appropriate Use Criteria for Cardiac Computed Tomography. Exclusion criteria will include patients who are not able to obtain angiography to include: previous anaphylactoid reaction to iodinated contrast material and renal insufficiency (verified by a renal panel within 30 days of the procedure).

In accordance with standard operating procedures for CCTA (joint Cardiology-Radiology program), patients will arrive to the cardiovascular preparation area (“Prep and Recovery”, Building 9A) and will receive a clinical assessment with vital signs by a physician and nursing staff. Patients without a contraindication to B-adrenergic blocking agents and/or calcium channel blocking agents (will be given a beta-blocker either by oral intake or intravenously prior to the exam to obtain a goal heart rate between 50-65 bpm). Once the patients are within this window they will be escorted to radiology, in accordance with standard CCTA policies. During the preparation time eligible patients will be consented by [name] and will be randomized at that time. The patient’s chart will have an envelope with it that describes which investigational arm the patient will be in. The radiologist and cardiologist will view the card in the envelope after making their initial decision on the parameters for the CCTA.

CT Protocol

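### Read literally, section 6.3 does not count symptomatic premedication reactions that begin and resolve in the preparation area, and its start rules agree neither with each other nor with section 6.4

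*Combined protocol and SAP*

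**What the plan says.** The safety monitoring plan in section 6.3 defines an adverse event broadly, as "any unfavorable and unintended sign, symptom, or disease temporally associated with the study procedures, whether or not considered related to the procedure". The next sentence narrows this for symptoms and signs: "Only symptoms/signs that begin, increase in frequency or worsen in severity after the procedure start will be considered as AEs". The sentence after that brings in symptom-free changes, with no start condition: "Any asymptomatic change from baseline such as results from diagnostic procedures (renal function or vital signs that is clinically significant". Neither the start of the procedure nor baseline is defined.

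Later in 6.3, unexpected adverse events and serious adverse events are recorded from a stated point: "After a subject starts his/her cardiac CT procedure and throughout" the period that follows. Active questioning about adverse events also begins with the CCTA procedure.

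Section 5.5 describes what happens before that. Patients arrive in the preparation area, have vital signs taken, and receive the heart-rate drug unless it is contraindicated. "Once the patients are within this window they will be escorted to radiology". Consent and randomisation take place during the same preparation time. Section 6.2 names the drug's harms: "These risks include: hypotension, bradycardia, dyspnea, wheezing, fatigue, diarrhea, GI disturbances and worsening of certain neurologic conditions". It says of these patients that "they will be monitored prior to and after the procedure by nursing staff".

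Section 6.4 requires the principal investigator to report serious adverse events in subjects enrolled at the centre within 24 hours. It does not make this depend on the CT having started.

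**The concern.** The drug with the listed harms is given before the point at which 6.3 starts to count symptoms and signs. A consented, randomised patient could have symptomatic hypotension, dyspnea or wheezing in the preparation area, recover before the scan, and have no adverse event under the stated rule.

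The research monitor, the medical monitor and the IRB all depend on these counts. At stake are the completeness of the total count and the status of a serious event that occurs during preparation. The point concerns recording only. It takes no position on the use of the drug.

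**Working it through.** The plan gives no figure to reproduce, so the check is to put the steps in time order and apply each rule to them.

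**Order of events (section 5.5).**
1. Arrival in the preparation area, clinical assessment and vital signs.
2. Heart-rate drug, consent and randomisation, all in the preparation period. The order of drug and consent is not stated.
3. Move to radiology once the heart rate is in range.
4. Imagers choose initial CCTA settings, using the achieved heart rate, and then open the allocation card.
5. Topograms, the randomised non-contrast scan, nitroglycerin, timing bolus and CCTA.

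**Where the window opens.** Section 6.3 ties the recording of unexpected and serious events to the cardiac CT, which is step 5. Section 6.2 describes nursing observation in the preparation area as coming before and after the procedure. The protocol's own usage therefore places step 2 outside the procedure.

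**Rules applied to four cases after consent.**

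| Case | Result |
|---|---|
| Symptomatic reaction that begins and resolves in preparation | Not an adverse event under the symptoms-and-signs sentence of 6.3 |
| Reaction that begins after the procedure starts, or begins earlier and then worsens or becomes more frequent | Counted |
| Symptom-free bradycardia or hypotension in preparation, clinically significant | Can count under the next sentence of 6.3, but against an undefined baseline |
| Serious event confined to preparation | Outside the recording window of 6.3, but reportable on the wording of 6.4 |

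The first and third rows sit oddly together. Symptom-free hypotension in the preparation area can count, while symptomatic hypotension there does not. Nitroglycerin gives a second contrast. It is also routine, but it is given after the non-contrast scan, so on the natural reading symptomatic hypotension from it is inside the window.

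The fourth row is a conflict between sections. Section 6.3 defines a serious adverse event as an adverse event that meets a seriousness criterion. If a symptomatic event fails the test for an adverse event, then read strictly it is not a serious adverse event either, and 6.4 would have nothing to act on. Read by its own words, 6.4 covers it.

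**Size.** The documents give no rate. Each 1% of the 175 planned subjects with a reaction of the first kind would be 175 × 0.01 = 1.75 events. At an assumed 1% to 5%, the count is 1.75 to 8.75 (175 × 0.05 = 8.75). These rates are assumptions for scale only.

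**Between arms.** The drug is given before the imagers see the allocation and before the arms differ in any way. The lost events should therefore fall about equally in the two arms.

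**The case against.** The strongest case on the other side is that the text is loosely worded and does not set out to exclude anything. The start of the procedure is undefined, and the general definition speaks of study procedures in the plural. Premedication is routine care, the modified scan is the only investigational component (section 6.2), and safety is not an endpoint (section 5.8). The data sheets in section 5.5.5 have adverse-event fields with no window.

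Much of this stands, and it rules out several stronger readings that a reader might infer:

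- *All the listed harms of the drug go uncounted.* They do not. Events that begin or worsen after the start count, and clinically significant symptom-free vital-sign changes can count at any time.
- *Any serious event in preparation is missed.* Section 6.4 has no CT-start limit and requires reporting even when the investigator thinks the event unrelated. The supportable claim is that 6.3 and 6.4 conflict.
- *A patient who never reaches the scanner appears only as a dropout.* The Patient Information Data Sheet has a field for adverse clinical events, and section 5.7.3 plans a flow diagram.
- *Section 6.3 itself promises to cover the drug's harms by naming procedure medications.* That clause only defines when an event is unexpected: "An AE that has not been previously reported for the investigational product (VCT scanner), any procedure medications, or any concurrent medications". The harms in 6.2 are already known.

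What the objection does not remove is the word that opens the symptoms-and-signs sentence. It is an explicit restriction, and an unrestricted data field does not change what is counted. Nor does the routine nature of the drug explain the split, because the definition includes events whether or not they are related.

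**Conclusion.** The point holds in a limited form. Read literally, 6.3 excludes symptomatic premedication reactions confined to the preparation area, even in consented and randomised patients. Its start rules are inconsistent within 6.3 and with 6.4.

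The consequence is an under-count of total adverse events, of unknown size, and an unclear status under 6.3 for serious events during preparation. A reader might also infer a biased safety comparison. The documents do not support that, because the arms do not differ until after the drug is given.

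The conclusion rests on two readings: that the procedure in 6.3 means the cardiac CT, as its recording sentence states, and that preparation comes before it, as 6.2 implies. It applies to events after consent. Where the drug precedes consent, an event may fall outside the study altogether.

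**What to change.** 1. In both start sentences of 6.3 (symptoms and signs; unexpected and serious events), replace the present start with: *from the first pre-scan preparation step after consent (first premedication dose or intravenous line placement)*. Leave the end of the window unchanged.
2. Define baseline in 6.3 as the vital signs taken on arrival under section 5.5.
3. Reconcile 6.3 with 6.4 so that both use the same start point for adverse and serious adverse events.
4. On the existing data sheet, record onset as before, or from the start of, the randomised non-contrast scan.
5. Report all events in the safety summary. For the research monitor's comparison between arms, use events with onset from the start of that scan, including those during it. A cut at the end of the scan would drop events that occur while it runs.

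The cost is a few sentences and one onset field. Vital signs and nursing observation in the preparation area are already in place, so no new visits or tests are needed. The downside is a slightly higher adverse-event count that includes reactions to routine premedication. The onset field lets these be shown separately.
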